### **11.1.2 Headache response**

Headache response is defined as a reduction in migraine headache pain intensity from severe or moderate at the time of initial treatment to mild or none at a specific assessment time. Headache response is a binary response variable (yes or no).

### **11.1.3 Resolution of associated symptoms of migraine**

Resolution of associated symptoms of migraine is defined for those patients who have associated symptoms at baseline who are then symptom free at the assessment timepoints. Associated symptoms of migraine are photophobia, phonophobia, nausea, or vomiting.

### **11.1.4 Time to use of rescue medication**

Time to use of rescue medication starts with the dosing time of study drug and ends with the first use of rescue medication. If an event has not occurred by the final assessment point, the response is considered censored for the purpose of analysis.

### **11.1.5 Ability to perform normal activities**

Ability to perform normal activities will be assessed before treatment, at 15 minutes and at 1, 2, 3, 4, and 24 hours post treatment in the patient's diary as follows by the question: "*Are you able to perform normal activities at this time?*" (yes/no).

### **11.1.6 Increase of intensity with movements**

Increase of migraine headache intensity by movement (yes/no) will be recorded before treatment, at 15 minutes and at 1, 2, 3, 4, and 24 hours post treatment in the patient's diary.

## **11.2 Calculation or derivation of safety variable(s)**

### **11.2.1 Other significant adverse events (OAE)**

During the evaluation of the AE data, an AstraZeneca medically qualified expert or its representative will review the list of AEs that were not reported as SAEs and discontinuations due to AEs. Based on the expert's judgment, significant AEs of particular clinical importance may, after consultation with the Global Drug Safety Physician, be considered OAEs and reported as such in the Clinical Study Report (CSR).

A similar review of laboratory, vital signs, and ECG data will be performed for identification of OAEs. Examples of these are marked hematological and other laboratory abnormalities, and certain events that lead to intervention (other than those already classified as serious), dose reduction, or significant additional treatment.

## **12. STATISTICAL METHODS AND SAMPLE SIZE DETERMINATION**

Statistical analyses will be conducted using SAS (Version 8.2 or above). A comprehensive statistical analysis plan (SAP) will be prepared before the interim analysis is conducted. The final version of the SAP will be attached as an appendix to the clean file document.

### **12.1 Description of analysis sets**

#### **12.1.1 Safety analysis set**

The safety analysis set includes all randomized treated patients who provide post-treatment safety data, classified according to the treatment actually received. Throughout the safety results sections, erroneously treated patients (eg, those randomized to treatment A, but actually given treatment B) will be accounted for in the actual treatment group. The analysis of all safety and tolerability variables will be performed using the safety analysis set.

#### **12.1.2 Full analysis set**

The full analysis set (FAS) includes all randomized treated patients who provide post-treatment efficacy data, classified according to randomized treatment. The analysis of all efficacy variables will be performed using the FAS.

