### **12.2 Methods of statistical analyses**

All statistical comparisons will be based on a 2-sided significance level of  $\alpha=0.05$  unless otherwise specified.

Descriptive statistics will be used to present efficacy and safety variables. For continuous variables, n, mean, standard deviation, median, minimum, and maximum will be presented. For categorical variables, n, frequency, and percentage will be presented.

Two types of datasets, both derived from the FAS, will be used for efficacy analyses: the observed case (OC) dataset and the last observation carried forward (LOCF) dataset. In general, the OC data for a visit will consist of the actual observations recorded for the visit. If missing, the OC data will remain missing – no data imputation will be performed. The LOCF data will be the corresponding OC data or, if that is missing, the last non-missing data carried forward from the most recent preceding assessment time. However, baseline values will not be carried forward for LOCF imputation. Baseline is defined as the last non-missing pre-treatment value. No other data imputation will be performed.

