### 12.2.2 Primary efficacy variable

The primary null hypothesis to be tested is that the different doses of zolmitriptan 0.5 mg, 2.5 mg and 5 mg are not different from placebo, using pain-free status at 2 hours post treatment as the primary variable.

The primary variable will be analyzed using a logistic regression model with 2-hour pain-free status as the response variable including treatment and center as fixed factors in the model. A step-down approach is used for maintaining the alpha level when comparing the 3 doses of zolmitriptan against placebo for 2-hour pain-free status. Initially, zolmitriptan 5 mg is compared with placebo in terms of odds ratio. If zolmitriptan 5 mg is significantly better than

placebo at the 2-sided 5% level, then zolmitriptan 2.5 mg is compared with placebo, and if it is significantly better than placebo at the 2-sided 5% level, then zolmitriptan 0.5 mg is compared with placebo. If the first comparison between zolmitriptan 5 mg and placebo is not significant, then the zolmitriptan 2.5 mg is not to be compared with placebo, etc. The primary analysis will be based on the FAS with the LOCF approach.

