### **12.3 Determination of sample size**

A total of 2400 patients will be enrolled to ensure 1000 randomized patients. This assumes a 56% drop-out rate prior to randomization. Assuming 20% of the randomized patients drop out before treatment of a headache attack, 800 patients (250, 150, 150, and 250 patients in the placebo, zolmitriptan 0.5 mg, zolmitriptan 2.5 mg, and zolmitriptan 5 mg treatment arms, respectively) will be evaluable for the primary analysis. This will give 80% power to detect a treatment difference at the 2-sided significance level of 0.05 if the true difference between a zolmitriptan 5 mg treatment and placebo in terms of difference in pain-free rates is 0.11 for the primary endpoint, 2-hour pain-free status. The power to detect a treatment difference between zolmitriptan 2.5 mg and 0.5 mg versus placebo will be 67% if the true treatment difference is 0.11. A 2-treatment, continuity-corrected, chi-square test of equal proportions is used as an approximation for the intended analysis approach in the power calculations. A difference of 0.11 in response rates is considered a clinically relevant effect. The pain-free rate for the placebo treatment group is assumed to be the same as in a previously conducted study (D1221C00005) on zolmitriptan nasal spray in adolescent patients for both periods combined, 0.18.

Since the assumptions for the sample size calculations are uncertain, an interim analysis is planned for after approximately one third of the planned patients have been treated. The sample size will be re-estimated at the interim analysis using a blinded estimation of the observed total 2-hour pain-free status. The sample size can increase depending on the interim results; the maximum number will be 1036 evaluable patients in total, ie, approximately 1295 patients need to be randomized and 2943 patients need to be enrolled.

The interim analysis will be performed by an independent statistician who is not involved with this trial.

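### The primary analysis (FAS with LOCF) lets post-dose diary completion decide which dosed patients are analysed and how they are scored at 2 hours

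*Protocol*

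**What the plan says.** Four rules in the protocol act together.

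- **Analysis set (12.1.2, repeated in the synopsis).** The FAS "includes all randomized treated patients who provide post-treatment efficacy data, classified according to randomized treatment". Taking study drug is not enough; the patient must also supply efficacy data after dosing.
- **Primary analysis (12.2.2).** "The primary analysis will be based on the FAS with the LOCF approach".
- **Imputation (12.2).** A missing value is replaced by the most recent earlier post-dose value. "However, baseline values will not be carried forward for LOCF imputation", and "No other data imputation will be performed".
- **Data source (6.1, 6.3.1, 6.5.1).** Pain intensity comes from a paper diary kept by the patient. Post-dose entries are due at 15 minutes and at 1, 2, 3, 4 and 24 hours, with a window of 20 minutes either side of the 2-hour entry.

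**The concern.** Leaving out patients who were randomized but never dosed is defensible under the double blind. Leaving out patients who were dosed is different, because the condition for inclusion is met after treatment and may depend on relief, distress or falling asleep. The rules produce three groups of dosed patients without a 2-hour record:

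1. **No post-dose record.** The patient is not in the FAS.
2. **First record after 2 hours.** The patient is in the FAS, but there is no earlier post-dose value to carry forward and nothing else is imputed. The patient has no 2-hour outcome and cannot enter the logistic model, so the analysed set is smaller than the named set.
3. **A 15-minute or 1-hour record only.** That value stands as the 2-hour outcome. An early pain score of none becomes a 2-hour success even if the headache came back. An early score of mild or worse becomes a failure even if the patient was pain-free by 2 hours.

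The 5 mg versus placebo comparison is at stake. It is the first step of the step-down procedure in 12.2.2, so a shift there affects whether the two lower doses are tested at all.

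**Working it through.** **Inputs from section 12.3:** placebo rate 0.18; difference 0.11, hence 0.29 on 5 mg; two-sided 0.05; continuity-corrected chi-square; 250 evaluable patients in each of the placebo and 5 mg arms.

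**Input not in the protocol:** the share m of dosed patients with no usable 2-hour value. I assume 2% to 5%, written m0 for placebo and m1 for 5 mg.

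**Step 1: the plan's own figures.** The continuity-corrected formula for 0.18 versus 0.29 at 80% power gives 250 per arm. Power is 80.0% for 250 versus 250 and 67.9% for 250 versus 150. Also 1000 × 0.80 = 800. The stated figures reproduce.

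**Step 2: bias when non-reporters are excluded and all of them are failures.**

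FAS difference = 0.29/(1 − m1) − 0.18/(1 − m0)

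| m0 (placebo) | m1 (5 mg) | FAS rates | Difference (true 0.110) |
|---|---|---|---|
| 2% | 2% | 0.296, 0.184 | 0.112 |
| 5% | 5% | 0.305, 0.189 | 0.116 |
| 2% | 5% | 0.305, 0.184 | 0.122 |
| 5% | 2% | 0.296, 0.189 | 0.106 |

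Within this range the shift runs from −0.004 to +0.012, and its sign depends on which arm loses more diaries.

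**Step 3: cost of scoring missing as not pain-free.** Keep 250 per arm, with equal missingness unrelated to outcome. The difference is 0.11 × (1 − m).

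- m = 2%: 0.1078, power 78.9%
- m = 5%: 0.1045, power 77.2%

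Against 80.0% this is a loss of 1.1 to 2.8 points.

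**Step 4: when the remedy itself misleads.** Suppose every non-reporter was in fact pain-free. Missing = failure then gives (0.29 − m1) − (0.18 − m0).

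- m0 = 2%, m1 = 5%: 0.24 − 0.16 = 0.08, power about 57%
- m0 = 5%, m1 = 2%: 0.27 − 0.13 = 0.14

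Excluding the same patients gives 0.24/0.95 − 0.16/0.98 = 0.089 and 0.27/0.98 − 0.13/0.95 = 0.139. In this adverse case the present rule is biased in the same direction and by nearly as much.

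**The case against.** **Missingness should be low.** Patients are randomized only after completing the run-in diary correctly (3.1, 5.2.1), likely compliance must be demonstrated in run-in (4.1, criterion 10), and diary instructions are repeated at Visit 2 and at the interim visit (3.1.2, 3.1.4). Sleep and rescue medication are prohibited for 2 hours after dosing (5.1), so sleeping through the 2-hour entry would usually be a protocol deviation. This stands: it makes a small bias likely, although it does not guarantee one.

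**LOCF errs in both directions.** Only an early score of none is carried as a success; any other early score is carried as a failure. This also stands, and is why no direction is claimed.

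**Sensitivity analysis is partly present.** Section 12.2 defines an observed-case dataset, and 12.2.3 lists 2-hour pain-free status among variables analysed by observed case and/or LOCF. However, neither dataset restores the excluded dosed patients, since both derive from the FAS.

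**Missing = failure is also an assumption.** True, as Step 4 shows. Its advantage is that every dosed patient is counted by a rule fixed in advance.

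**Two stronger readings are tempting but not supported.**

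- A reader might infer that the sample size is wrong, because 12.3 places the whole loss before dosing ("Assuming 20% of the randomized patients drop out before treatment of a headache attack, 800 patients") and so treats every dosed patient as evaluable. But the targets are stated as evaluable patients and the arithmetic reproduces. Losing 2-5% of dosed patients would leave power at about 79-78%. The fix below does not change the sample size.
- A reader might infer material inflation of the type I error. Reaching about 6% takes 5% versus 10% missing, all non-reporters failures, and an uncorrected test. With the continuity correction the same case gives about 4.5%. The protocol supplies no missing rates that would support such a claim.

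**Conclusion.** The point holds as a modest weakness in the primary analysis. The rules are fixed in the protocol, and together they let diary behaviour after dosing decide whether a dosed patient is analysed and from which time point. No other section restores these patients to the primary analysis.

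The likely effect is small and its direction is unknown. With true rates of 0.18 and 0.29 and non-reporters all failures, unequal missingness within 2-5% moves the 5 mg difference from 0.110 to between 0.106 and 0.122. These are illustrations under assumed missing rates, not estimates. They cover excluded patients only; the error from carrying forward early scores cannot be sized from the protocol.

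**What to change.** - **Section 12.1.2 and the synopsis:** define the primary efficacy set as all randomized patients who took study drug, classified by randomized treatment.
- **Section 12.2.2 and the synopsis:** for the primary analysis, score any such patient without a 2-hour headache record inside the 6.5.1 window as not pain-free.
- **Sensitivity analyses:** keep the FAS with LOCF and the observed-case analysis, and report missing 2-hour records by arm so that a reader can judge whether missing = failure matters.

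The change is about two sentences and one derivation rule. Pain-free rates fall slightly in every arm, at the power cost shown in Step 3. The remaining risk is the Step 4 case, where non-reporters were pain-free and missingness differs by arm; that is the reason for keeping the other analyses.

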### **12.2 Methods of statistical analyses**

All statistical comparisons will be based on a 2-sided significance level of  $\alpha=0.05$  unless otherwise specified.

Descriptive statistics will be used to present efficacy and safety variables. For continuous variables, n, mean, standard deviation, median, minimum, and maximum will be presented. For categorical variables, n, frequency, and percentage will be presented.

Two types of datasets, both derived from the FAS, will be used for efficacy analyses: the observed case (OC) dataset and the last observation carried forward (LOCF) dataset. In general, the OC data for a visit will consist of the actual observations recorded for the visit. If missing, the OC data will remain missing – no data imputation will be performed. The LOCF data will be the corresponding OC data or, if that is missing, the last non-missing data carried forward from the most recent preceding assessment time. However, baseline values will not be carried forward for LOCF imputation. Baseline is defined as the last non-missing pre-treatment value. No other data imputation will be performed.

#### **12.2.1 Interim analyses**

An interim analysis will be performed based on the results of approximately 267 evaluable patients. Furthermore, available data from the diary will be included in the interim analysis for a sample size re-estimation calculation.

The sample size re-estimation (SSR) will be based on blinded data, ie, the pooled response rate of the primary variable, pain-free status at 2 hours. The clinically relevant treatment effect of 0.11 difference in response rates, 80% power and a 2-sided significance of 0.05 will be used. An approximative method based on the 2-treatment, continuity-corrected, chi-square test of equal proportions (Friede and Kieser 2006) will be used as a approximation for the intended analysis approach in the power calculations. Friede and Kieser 2006 discuss the 2-sample parallel group design; however, in this case since pairwise comparisons will be the primary analysis, this method can be used for this 4-sample parallel group design. For further detail please refer to the Friede and Kieser article.

$$N/\text{arm}_{\text{SSR}} = \left(2 + \theta + \frac{1}{\theta}\right) \cdot \frac{(z_{1-\alpha/2} + z_{1-\beta})^2}{2 \cdot (\Delta^*)^2} \pi \cdot (1 - \pi)$$

$\theta = 1$  with a balanced design

$\Delta^*$  clinically relevant difference

$z_{1-\alpha/2}$  1.96 with a  $\alpha$  – level = 0.05 2 – sided

$z_{1-\beta}$  0.842 with power( $\beta$ ) = 0.8

$\pi$  the estimated total response rate

The estimated sample size (N/arm) will be used for the zolmitriptan 5 mg and placebo treatment arms. The 2 lower dose treatment arms, zolmitriptan 2.5 mg and zolmitriptan 0.5 mg, will be assigned to patients at a ratio of 5:3:3:5 (placebo:zolmitriptan 0.5 mg:zolmitriptan 2.5 mg:zolmitriptan 5 mg) at randomization. The estimated sample size obtained from the analysis are rounded up to the nearest larger integer and should not be rounded any further. The total sample size after the SSR will be  $N_{\text{Total}} = 2 \cdot N/\text{arm}_{\text{SSR}} + 2 \cdot 3/5 \cdot N/\text{arm}_{\text{SSR}}$ . The maximum sample size required after the SSR will be  $2 \cdot 324 + 2 \cdot 3/5 \cdot 324 = 1036$  evaluable patients. The sample size will not decrease from the original sample size.

More details will be specified prior to the interim analysis in a DMC charter. No adjustment for the significance level will be done since the analysis is preformed on blinded data and there is no analysis assessing the efficacy.

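### The re-estimation formula in 12.2.1 is described as continuity-corrected but is not, so it rests on a different basis from the original 250 per arm

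*Protocol*

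**What the plan says.** Section 12.3 sizes the trial at 250 evaluable patients each on placebo and 5 mg, and 150 on each lower dose. The placebo rate comes from a previous study "for both periods combined, 0.18", and the difference to detect is 0.11. Of the 5 mg comparison it says: "This will give 80% power to detect a treatment difference at the 2-sided significance level of 0.05". The stated basis is that a "2-treatment, continuity-corrected, chi-square test of equal proportions is used as an approximation for the intended analysis approach in the power calculations".

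Section 12.2.1 re-estimates the size after about 267 evaluable patients, from the blinded pooled 2-hour pain-free rate. The targets are unchanged: "The clinically relevant treatment effect of 0.11 difference in response rates, 80% power and a 2-sided significance of 0.05 will be used". The method is named as "An approximative method based on the 2-treatment, continuity-corrected, chi-square test of equal proportions", and a formula with all its constants is printed. The protocol argues that, because the comparisons are pairwise, "this method can be used for this 4-sample parallel group design". The result is to be "rounded up to the nearest larger integer and should not be rounded any further". The size may not fall below the original. The ceiling is 324 per main arm, and section 12.3 repeats that "the maximum number will be 1036 evaluable patients in total".

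**The concern.** Both sections name the same continuity-corrected test, so a reader expects the original and re-estimated sizes to be on one scale. The printed formula looks like the ordinary normal-approximation formula with no continuity term. If so, the trial is sized on one basis and re-sized on a less demanding one under the same name. The re-estimation exists because the planning assumptions are called uncertain, so the power it delivers when the placebo rate is above 0.18 should be stated correctly.

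A second question is the rate entered. The result sizes 5 mg against placebo, but the rate is pooled over four arms in the ratio 5:3:3:5.

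**Working it through.** **Inputs.** From 12.3: placebo 0.18, difference 0.11 (so 0.29 on 5 mg), 250 and 150 per arm. From 12.2.1: z-values 1.96 and 0.842, theta = 1, floor at the original size, cap 324 per main arm. Allocation 5:3:3:5. Placebo rates other than 0.18 and all low-dose effects used below are assumptions.

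**Step 1: which basis gives the original figures?** Two-proportion power with and without the continuity correction (the low-dose rows use 250 v 150):

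| Comparison | Stated | Corrected | Uncorrected |
|---|---|---|---|
| 250 v 250, difference 0.11 (12.3) | 80% | 80.0% | 82.9% |
| 250 v 150, difference 0.11 (12.3) | 67% | 67.9% | 72.1% |
| 250 v 150, difference 0.15 (3.2) | 90% | 90.2% | 92.1% |
| 250 v 250, difference 0.15 (3.2) | 96% | 96.5% | 97.2% |

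The stated powers fit the corrected calculation. The original design is continuity-corrected, as it says.

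**Step 2: the printed formula.** With theta = 1 it is N = 4 × (1.96 + 0.842)² / (2 × 0.11²) × π(1 − π). The usual correction is N/4 × (1 + √(1 + 4/(N × 0.11)))².

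| π | Printed formula | With correction |
|---|---|---|
| 0.235 (mean of 0.18 and 0.29) | 233.3 | 251.2 |
| 0.26 | 249.7 | 267.6 |
| 0.30 | 272.5 | 290.4 |
| 0.50 | 324.4 | 342.4 |

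The 324 cap is the printed formula at π = 0.5, so the cap is uncorrected too. At 0.235 the formula gives 234 after rounding up. The corrected method gives 252 by this formula, or 250 when the two arms' separate variances are used. The printed formula reaches 250 only at π of about 0.2605, so below that the floor decides and no patients are added. The gap to the corrected size is about 18 per main arm throughout.

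**Step 3: power after re-estimation, pooled rate equal to the placebo/5 mg mean.** True difference 0.11, floor and cap applied:

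| Placebo rate | N per main arm | Corrected | Uncorrected |
|---|---|---|---|
| 0.18 | 250 (floor) | 80.0% | 82.9% |
| 0.20 | 250 (floor) | 77.8% | 80.8% |
| 0.22 | 259 | 77.4% | 80.2% |
| 0.25 | 276 | 77.6% | 80.3% |
| 0.30 | 298 | 77.8% | 80.3% |
| 0.445 | 324 (cap) | 77.8% | 80.1% |

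**Step 4: effect of the four-arm rate.** With placebo rate p and a 0.11 effect of 5 mg, the two-arm mean is p + 0.055. The four-arm rate is p + 0.11 × 5/16 = p + 0.034 if the low doses are inert (0.021 too low), and p + 0.11 × 11/16 = p + 0.076 if all doses have the 0.11 effect (0.021 too high).

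- Low doses inert: corrected power is 75.8% at placebo 0.22 to 0.25 and 76.5% at 0.30. Uncorrected it is 78.8%, 78.7% and 79.1% at 0.22, 0.25 and 0.30.
- All doses at 0.11: corrected power is 79.5% at placebo 0.20, 79.3% at 0.22, 79.0% at 0.25 and 78.8% at 0.30. Uncorrected it falls from 82.3% to 81.2% over that range.

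**Step 5: rounding of the cap.** 324.4 rounded up is 325, and 3.2 × 325 = 1040. The plan uses 324, and 3.2 × 324 = 1036.8 is shown as 1036.

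**The case against.** The strongest reply is that the shortfall is measured on a test the trial will not run. Section 12.2.2 makes logistic regression the primary analysis, and the corrected chi-square is only an approximation to it. A Wald test of the log odds ratio carries no continuity correction. Simulated without center, it gives about 80% power at 250 per arm (mean rate 0.26) and at 273 per arm (mean rate 0.30). This stands: for the planned analysis the uncorrected formula comes close to its target, and the original 250 is mildly generous. It does not remove the mismatch, because the plan names the corrected basis in both sections and follows it in only one.

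A reader might infer that the re-estimated trial always has about 76-78% power instead of 80%. The documents do not support that. At the plan's own rates the floor keeps 80.0%, and if all doses have the 0.11 effect that section 12.3 uses for the low-dose power, corrected power can reach 79.5%. The 75.8% figure needs inert low doses and a placebo rate of 0.22 to 0.25, neither of which the plan assumes.

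A reader might also infer that the four-arm rate is an error with a known direction. It is not. The bias runs from −0.021 to +0.021 with the unknown low-dose effects, and the standard error of a rate of 0.235 from 267 patients is about √(0.235 × 0.765/267) = 0.026. A fixed conversion would rest on guesses. With 0.11 for both low doses it would lower the rate entered by 0.021 and shrink the sample.

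The cap rounding is trivial. The round-up rule can be read as applying to the interim result and not to a preset ceiling, and one patient per arm moves power by about 0.1 point.

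**Conclusion.** The point holds as an inconsistency of basis. Section 12.2.1 names a continuity-corrected method and prints an uncorrected formula and cap, while 12.3 is continuity-corrected. The cost is nil at 0.18 and 0.29. Above the planned placebo rate, with the pooled rate equal to the two-arm mean, corrected power is about 77-78% and uncorrected power about 80%. Allowing for the four-arm rate, corrected power runs from about 76% to 79.5%, and uncorrected power from about 79% to 82%. These ranges assume a true 0.11 difference for 5 mg, together with the placebo rates and low-dose effects shown. The blinded re-estimation's type I error and the treatment estimate are not in question. Severity is minor to moderate: a stated basis and power need correcting, but the trial is not materially underpowered for its planned analysis.

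**What to change.** Put 12.2.1 and 12.3 on one basis before the interim analysis, in one of two ways.

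1. Remove the continuity-correction label from 12.2.1, and state that the re-estimated size targets 80% uncorrected power, about 77-78% on the corrected basis of 12.3. This costs wording only.
2. Keep the label and add the correction N/4 × (1 + √(1 + 4/(N × 0.11)))² to the formula, with a cap of about 343 per main arm (3.2 × 343 = 1097.6, so about 1,098 evaluable). This costs up to about 18 more evaluable patients per main arm, with the lower-dose arms rising at 3/5 of that. At 20% drop-out the maximum randomized would be about 1097.6/0.8 = 1,372, against 1,295 now.

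Under either option, add a short table, in the protocol or the DMC charter, showing how the re-estimated size and power vary with the low-dose effects, since the input is the four-arm rate. Do not fix a conversion on assumed low-dose effects.

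As a minor tidy-up under the first option, either let the cap follow the round-up rule (325 per main arm, 1040 in total) or call 324 and 1036 a preset ceiling.
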